6.3 Screening

At the screening visit the PI or a delegated co-investigator or sub-investigator will discuss the trial with the patient in detail; potential participants will be encouraged to ask any questions in relation to the study and their concerns will be addressed and clarified. Patients may take additional time to consider their participation following this discussion and return at a later date to provide written, informed consent if they wish. Following this process, patients wishing to participate in the trial will provide written, informed consent by signing and dating the trial Consent Form. At the time of consent, participants must be informed that they have the right to withdraw their participation in the trial at any stage and that doing so will not

prejudice their future clinical management and care. The right of the patient to refuse consent without giving reasons will be respected. Informed consent will be taken by an appropriate member of the study team. The original consent will be filed in the Investigator Site File; a copy of the consent will be given to the patient, and one filed in the hospital notes.

As per the study visit schedule, screening will entail evaluation of:

- Inclusion and exclusion criteria
- Demographic data including age, gender and race
- Medical history, comorbidities and concomitant medications
- Physical examination: vital signs, 66/68 joint count
- Urine sample will be taken for dipstick testing (glucose, blood and protein)
- Blood tests (ESR, CRP, CBC, serum creatinine, coagulation screen and INR)
- Females will be required to carry out a pregnancy test
- Patient general health VAS (DAS28)

If necessary, patients may be invited to return within 10 days of their screening visit for one or more of their screening tests to be repeated – these may include any combination of serum creatinine, CBC, coagulation screen, INR or urine dipstick.

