5.2.2 Exclusion criteria

- Serum creatinine that is above the upper limit of normal at baseline
- Patients who have received oral, intravenous, intramuscular (IM) or intra-articular glucocorticoid drugs within 4 weeks of their baseline visit (glucocorticoids administered via other routes such as inhaled, topical or intranasal will be permitted)
- Patients will be excluded if they have any contraindications to Tofacitinib which include:

- Pregnancy and lactation
- Women of Childbearing Potential (WOCP) who are not prepared to use effective contraception during treatment with Tofacitinib and for at least 4 weeks after the last dose
- Severe Hepatic impairment (Child Pugh C)
- Active TB, serious infections such as sepsis or opportunistic infections as detailed in the SmPC
- Chronic infections (HIV, Hepatitis B, Hepatitis C)
- Participants will be excluded if they have any contraindications to muscle biopsies. These include:
 - Participants on anticoagulant therapy. These include Vitamin K antagonists, Thrombin inhibitors, and Heparin and Low Molecular Weight Heparin preparations
 - Participants on antiplatelet. *Participants on Aspirin for primary prevention will be included in this study. However, Aspirin will be held for 7 days prior to the muscle biopsies and recommenced 48 hours after
 - Participants who are known to have bleeding disorders. These include, but are not limited to, Haemophilia, Factor II, V, VII, X, or XII deficiencies and Von Willebrand's disease
 - Previous reactions to local anaesthetics
 - Platelet count <100x10⁹/L
- Participants will be excluded if they have any contraindications to MRI. These include:
 - limb metal pins, plates, rods of screws that were placed less than 6 weeks from scanning day
 - heart pacemaker or replacement valves
 - neuro-stimulator or programmable intra-cerebral shunt, cerebral aneurysm clips
 - metallic foreign body in their eye
 - internal hearing devices, ocular prosthesis
 - weight >190 kg
 - claustrophobia

6 Trial Events

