6.1 Trial flowchart and schedule of visits

Schedule of events (all will take place either in the clinical research facility, the Newcastle Magnetic Resonance Centre or the Freeman Hospital):

	Visit 1 (Screening)	Visit 2 a-b (Investigations)	Visit 3 (Baseline – within 4 weeks of visit 1)	Visit 4 (1 month from visit 3 ± 3 days)	Visit 5 (6 months from visit 3 ± 7 days)	Early withdrawal visit
Informed consent	Х					
Inclusion and exclusion criteria	x					
Medical history	Х		Х	Х	Х	X
Concomitant medications	X		X	Х	х	X
Adverse events			Х	Х	Х	X
Physical examination	х		Х	Х	Х	X
Vital signs	Х		Х	Х	Х	X
Urinalysis (dipstick)	Х		Х	Х	Х	X
СК			Х	Х	Х	X
AST			Х	Х	Х	X
Myoglobin			Х	Х	Х	X
Cystatin C			Х	Х	Х	X
LDH			Х	Х	Х	X
ESR	Х		Х	Х	Х	X
CRP	Х		Х	Х	Х	X
CBC/FBC	Х				Х	X**
Creatinine	Х		Х	Х	Х	X
Coagulation screen and INR	Х				Х	X**
Pregnancy test	Х					
Circulating cytokines			X	Х	Х	X

	1			1		
STAT1/3			Х	Х		X
phosphorylatio						
n						
66/68 joint	Х		Х	Х	Х	X
counts						
Health			Х	Х	Х	X
assessment						
questionnaire						
disability index						
Patient global			Х	Х	Х	X
assessment VAS						
(ACR)						
Physician global			X	Х	Х	X
assessment VAS						
(ACR)						
Pain VAS (ACR)			X	Х	Х	X
Patient general	Х		Х	Х	Х	X
health VAS						
(DAS28)						
Muscle			Х	Х	Х	X
strength and						
gait speed						
testing						
Rapid			X		Х	X
assessment of						
physical activity						
questionnaire						
Consent for		Х			Х	X**
procedure						
DEXA*		Х		Х	Х	X**
Magnetic		X		Х	Х	X**
resonance						
spectroscopy *						
Accelerated		X		Х	Х	X**
MRI of selected						
limb*						
Muscle biopsy			Х		Х	X**
Clinical	х		X	Х	X	X
consumables						
Patient's meal			X		Х	X
				1.5		

*MRS/MRI and DEXA will take place in the Newcastle Magnetic Resonance Centre and Freeman Hospital respectively **In the event of early withdrawal, these activities will only be repeated if at least 3 weeks has elapsed since the original imaging or biopsy was performed All Participants will follow the visit schedule summarised in the Schedule of Events. If participants cannot attend on the due date, flexibility with a window on either side of the assessment due date will be permitted, as indicated.

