6.2 Identification and Recruitment

Potential participants will be identified and recruited at routine out-patient clinics at the Freeman Hospital. Identification may be extended to Patient Identification Centres (PIC sites) at surrounding hospitals. Potential participants will initially be identified by clinical or nursing staff responsible for routine care. They will be patients with active RA, in whom a decision has been taken to prescribe tofacitinib for their rheumatoid arthritis, in accordance with NICE guidelines; they will also have evidence of systemic inflammation as defined by the CRP criteria in section 5.2.1. If they are potentially interested in research participation then they will be contacted by a member of the research team and provided with a participant information sheet (PIS); consent to contact will also be sought (either signed on the day or signed later and posted back to the department) to allow a follow-up telephone call in 1-2 working days and an appointment for the screening visit to be arranged if the patient is interested in participation. Potential participants who decline participation will have anonymised information recorded in a screening log (age, gender, ethnicity, the reason not eligible for trial participation, or if they are eligible but declined). Potential participants identified at PIC sites will be contacted by a research nurse by telephone in the first instance and have a PIS mailed to them; they will be offered the opportunity to discuss the study faceto-face.

Potential participants who remain interested in the study after receiving a PIS, and having had an opportunity to discuss the study, will be given an appointment to attend the clinical research facility for a screening visit (see schedule of events). Patients may also be recruited from a dedicated research clinic in the Freeman Hospital; if patients in this clinic have had at least 1 day to consider participating since receiving a PIS then informed consent will be sought and the screening visit can take place on the same day. Patients who have not had this time to consider the study but remain interested will be contacted again within 1-2 working days to follow-up and discuss whether they would like to participate.

Participants will be reimbursed for reasonable travel expenses for all visits that take place outside of their routine care.

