6.4 Visit 2a-b

Following the confirmation of the participant's eligibility, Visits 2a and 2b will occur where MR imaging/spectroscopy (performed at the Newcastle Magnetic Resonance Centre) and the DEXA scan (performed at the Freeman Hospital) will take place respectively.

6.5 Baseline visit – Visit 3

The baseline visit will take place within 4 weeks of the screening visit in the CRF. At the end of this visit, patient will be instructed that they can start to take their NHS-prescribed Tofacitinib. Depending upon local arrangements and participant's preference, visits 2a-b and baseline may be conducted separately or combined into 1 or 2 visits. However, muscle biopsy must be performed after imaging and baseline tests have been completed.

Eligibility will first be confirmed, in particular incorporating the results of blood tests taken at the screening visit. In addition, the participant will undergo the following assessments:

- Medical history will be revisited including adverse events since screening
- Physical examination
- CK, AST, myoglobin, cystatin C , LDH, circulating cytokines and STAT1/3 phosphorylation bloods in addition to ESR and CRP
- Questionnaires will be completed by the participant or physician as appropriate including the Rapid assessment of physical activity (RAPA) questionnaire
- Muscle strength and gait speed testing
- Consent for procedure
- Initial muscle biopsy

6.6 Visit 4

The following visit will take place in the CRF 1 month after baseline visit. In this visit:

- Medical history will be updated, including adverse events, intercurrent illnesses and medications
- Physical examination will be repeated including vital signs and 66/68 joint counts.
- Questionnaires will be completed either by the participant or by the physician as appropriate
- A urine sample will be collected for urinalysis (dipstick)
- Blood samples will be collected as per schedule of events
- DEXA scan will be performed at the Freeman Hospital
- Magnetic resonance imaging and spectroscopy will be repeated at Newcastle Magnetic Resonance Centre
- Muscle strength and gait speed testing will be repeated

6.7 Visit 5

The final study visit, Visit 5 at 6 months after baseline, essentially recapitulates Visits 2 and 3. As before, patients will be given the choice of undergoing the investigations over 2 or 3 days or completing them all in one day (however all Visit 5 activities must be completed within 7 days of the due date i.e. 6 months after Visit 3).

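### The only scheduled pregnancy test can be 28 days old when the study tells a participant she can start tofacitinib

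*Protocol*

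**What the plan says.** Section 5.2.2 of the Protocol introduces one group of exclusions with "Patients will be excluded if they have any contraindications to Tofacitinib which include", and pregnancy and lactation head that list. The same list excludes women of childbearing potential who are "not prepared to use effective contraception during treatment with Tofacitinib and for at least 4 weeks after the last dose".

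The test that supports the pregnancy exclusion is a screening item in section 6.3: "Females will be required to carry out a pregnancy test". In the schedule of events (section 6.1), the row "Pregnancy test" has a single mark, under Visit 1.

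Section 6.5 sets the timing of Visit 3: "The baseline visit will take place within 4 weeks of the screening visit in the CRF". It also says what happens when the visit closes: "At the end of this visit, patient will be instructed that they can start to take their NHS-prescribed Tofacitinib". The assessments listed for Visit 3 do not include a pregnancy test. The section does require eligibility to be confirmed first, with emphasis on the screening blood results, and the medical history to be revisited.

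Section 6.2 describes candidates as patients "in whom a decision has been taken to prescribe tofacitinib for their rheumatoid arthritis", so the prescribing decision comes before recruitment.

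**The concern.** The exclusion is there to stop a pregnant woman from starting tofacitinib in the study. It has to hold at the end of Visit 3, when the study releases her to start, but the evidence for it was collected at Visit 1. Pregnancy status can change in that interval. A woman who conceives after screening and does not yet know it could pass through Visit 3 with every scheduled step completed, and then be told she can take a drug that the protocol lists as contraindicated for her.

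What is at stake is participant safety. The sample size, the endpoints and the analysis are not touched. The period after the first dose is also outside this point, because from then on the contraception criterion is the protocol's stated control.

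**Working it through.** The protocol gives no figure to reproduce here. The check is to set the provisions side by side and work out the interval.

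**Inputs**

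| Item | Value | Source |
|---|---|---|
| Pregnancy tests scheduled at Visit 1 | 1 | 6.1, 6.3 |
| Pregnancy tests scheduled at Visits 2a-b, 3, 4, 5 and early withdrawal | 0 | 6.1, 6.5 to 6.7 |
| Longest time from screening to Visit 3 | 4 weeks | 6.5, schedule header in 6.1 |
| Release to start the drug | end of Visit 3 | 6.5 |
| Planned sample | 15 | Synopsis, 9.1 |
| Women of childbearing potential | not given; assumed 0 to 15 | assumption |

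**Interval**

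- Longest age of the test at release = 4 weeks × 7 days = 28 days. This is a ceiling. No minimum gap is set, so an earlier Visit 3 shortens it.
- With a test at Visit 3, the age of the test at release = 0 days.
- Both figures are ages of a test. Neither is a probability of conception.

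**Does another provision cover the interval?**

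1. *Eligibility check at Visit 3 (6.5).* It is not limited to the screening bloods, so it does reach the pregnancy criterion. With no new test listed, it can draw only on the screening result and the history, and would find only a pregnancy that is known or suspected. In the schedule, the inclusion and exclusion row is marked at Visit 1 alone.
2. *Repeat screening tests (6.3).* These are allowed within 10 days of screening. The tests named are creatinine, blood count, coagulation screen, INR and dipstick. The pregnancy test is not named.
3. *Urine dipstick.* The schedule marks it at Visit 3, but 6.3 defines it as glucose, blood and protein.
4. *Contraception criterion (5.2.2).* It runs from treatment to at least 4 weeks after the last dose. As worded it does not start at screening, so testing and contraception leave the same interval open.
5. *Prescriber's checks.* None is named. A test made at the prescribing decision would precede recruitment (6.2), and so would be older than the screening test.

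Serum creatinine is a useful comparison. Its exclusion limit in 5.2.2 is set at baseline, and the schedule measures it again at Visit 3. Pregnancy can also change within 4 weeks and is not retested.

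**The case against.** The strongest objection is that this is a preference for one more test. Nothing in the protocol is contradictory: pregnancy is excluded, and a test is required of all females at screening. The study is observational. It neither chooses nor supplies tofacitinib, which the clinical team prescribes under its licence and NICE criteria. Section 8 states that, from this perspective, the risk does not exceed that of standard care. Silence about the prescriber's own checks does not show that they are absent. At Visit 3 eligibility is confirmed, and nothing stops an investigator with any doubt from retesting.

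Much of this stands and keeps the point small. It does not remove it. The prescribing decision is taken before recruitment, and the study itself gives the signal to start, so the study controls the moment at which the exclusion has to be true. Staff who followed the schedule to the letter would have no step that detects an unrecognised pregnancy.

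Two narrower objections deserve an answer.

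- *A test on the day is not complete protection.* This is correct. A very recent conception can test negative, and the first dose may be taken some time after the instruction. The change makes the test current; it does not bring the risk to zero.
- *Pregnancy is not among the listed contraindications to biopsy, so the biopsy need not wait for the result.* The reason to wait is different. The biopsy is done only for the study, eligibility is to be confirmed first at Visit 3, and a woman who has become ineligible should not undergo it.

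**Conclusion.** The concern holds, as a minor safety gap in the visit schedule that is cheap to close. The only scheduled pregnancy test can be up to 28 days old when the study tells a participant that she can start tofacitinib, and no other provision in the protocol tests for pregnancy in that interval.

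The size in participants cannot be fixed from the protocol. It depends on how many of the 15 are women of childbearing potential (assumed range 0 to 15), on how soon Visit 3 follows screening, and on whether the prescribing team tests separately. No estimate of the chance of conception is offered.

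**What to change.** For women of childbearing potential:

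- add a urine pregnancy test to the Visit 3 assessments in section 6.5, and mark it in the Visit 3 column of the schedule in section 6.1;
- require a negative result before the muscle biopsy and before the instruction to start tofacitinib;
- keep the screening test as it is.

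The cost is 1 test per woman × 0 to 15 women = 0 to 15 tests over the whole study. No visit or sample is added, because the schedule already has urine collected at Visit 3 for the dipstick. The order of the visit need not change: section 6.5 already places the biopsy after the baseline tests, so the result can be read before it.

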6.4 Visit 2a-b

Following the confirmation of the participant's eligibility, Visits 2a and 2b will occur where MR imaging/spectroscopy (performed at the Newcastle Magnetic Resonance Centre) and the DEXA scan (performed at the Freeman Hospital) will take place respectively.

6.5 Baseline visit – Visit 3

The baseline visit will take place within 4 weeks of the screening visit in the CRF. At the end of this visit, patient will be instructed that they can start to take their NHS-prescribed Tofacitinib. Depending upon local arrangements and participant's preference, visits 2a-b and baseline may be conducted separately or combined into 1 or 2 visits. However, muscle biopsy must be performed after imaging and baseline tests have been completed.

Eligibility will first be confirmed, in particular incorporating the results of blood tests taken at the screening visit. In addition, the participant will undergo the following assessments:

- Medical history will be revisited including adverse events since screening
- Physical examination
- CK, AST, myoglobin, cystatin C , LDH, circulating cytokines and STAT1/3 phosphorylation bloods in addition to ESR and CRP
- Questionnaires will be completed by the participant or physician as appropriate including the Rapid assessment of physical activity (RAPA) questionnaire
- Muscle strength and gait speed testing
- Consent for procedure
- Initial muscle biopsy

6.6 Visit 4

The following visit will take place in the CRF 1 month after baseline visit. In this visit:

- Medical history will be updated, including adverse events, intercurrent illnesses and medications
- Physical examination will be repeated including vital signs and 66/68 joint counts.
- Questionnaires will be completed either by the participant or by the physician as appropriate
- A urine sample will be collected for urinalysis (dipstick)
- Blood samples will be collected as per schedule of events
- DEXA scan will be performed at the Freeman Hospital
- Magnetic resonance imaging and spectroscopy will be repeated at Newcastle Magnetic Resonance Centre
- Muscle strength and gait speed testing will be repeated

6.7 Visit 5

The final study visit, Visit 5 at 6 months after baseline, essentially recapitulates Visits 2 and 3. As before, patients will be given the choice of undergoing the investigations over 2 or 3 days or completing them all in one day (however all Visit 5 activities must be completed within 7 days of the due date i.e. 6 months after Visit 3).

The following activities will be undertaken:

- Medical history will be updated, including adverse events, intercurrent illnesses and medications
- Physical examination will be repeated, including vital signs and 66/68 joint count
- Questionnaires will be completed either by the participant or by the physician as appropriate
- Blood samples will be collected as per schedule of events
- DEXA scan (at the Freeman hospital) and accelerated MRI and MRS (at the Newcastle MR centre) will be performed
- Muscle strength and gait speed testing will be repeated
- The second muscle biopsy will be taken

After visit 5 the participant's consultant rheumatologist will be contacted by letter and by telephone to inform them that the patient has completed study participation. Tofacitinib, if effective, will continue to be prescribed within the NHS.

6.8 Withdrawal criteria

Participants may withdraw from the study at any point without the requirement for any further involvement. If a participant wishes to withdraw from certain aspects of follow-up (e.g. repeat muscle biopsy) but to continue with other study assessments, this will be

permitted and encouraged. The PI may also withdraw patients from the study for medical reasons.

Participants who fail screening will be replaced but participants who drop out after the baseline visit will not be replaced. Where there is appropriate consent, their data will be used within the study report.

Participants who discontinue tofacitinib after visit 4, for whatever reason, will be invited to attend for an early withdrawal visit at the earliest opportunity. Participants will be encouraged to undergo the full range of study assessments if willing to do so but, if a participant wishes to decline some procedures but undergo others, this will be permitted and encouraged. Participants may also decline an early withdrawal visit in toto. At the discretion of the PI, aspects of the early withdrawal visit may be omitted depending on the time interval since they were last performed.

6.9 Changes to treatment

Tofacitinib will be prescribed as 5mg twice daily, the approved dose for rheumatoid arthritis.

If there are adverse effects relating to tofacitinib, the PI may discontinue the drug for 1 week before restarting, potentially at a dose of 5mg once daily with subsequent escalation to 5mg twice daily, subject to PI's discretion.

In the event of unforeseen events such as intercurrent illness or surgery, it may be necessary for participants to temporarily suspend tofacitinib and other medications and this will be managed as per standard clinical practice.

If participants have significant persisting arthritis symptoms, adjustments to background DMARD therapy are permitted at PI's discretion. Two intra-articular glucocorticoid injections are permitted (two on one occasion or one on two occasions). If additional escape therapy is required, such as substitution of an alternative JAK inhibitor or biologic therapy, or administration of oral or IM glucocorticoid, the participant will be withdrawn from the study and an early withdrawal visit triggered.

Any adjustments to treatment such as those described above will be managed according to standard clinical practice and documented at the study visits.

7 Study Procedures

